## 1. Background and Rationale

Anterior cruciate ligament (ACL) injuries are among the most common knee injuries in young athletes. Reconstruction using a bone–patellar tendon–bone (BPTB) autograft remains a widely accepted technique. However, donor site morbidity, including sensory deficits and anterior knee pain, are frequent complications. Platelet-rich fibrin (PRF), an autologous biological product, has been suggested to improve wound healing and potentially reduce donor site complications. This study was designed to investigate whether PRF can reduce sensory deficits and improve functional outcomes after ACL reconstruction with BPTB autograft.

## 2. Objectives

Primary Objective: To evaluate the effect of PRF application on sensory disturbances at the donor site 12 months after ACL reconstruction.

Secondary Objectives: To assess MRI healing of the donor site, functional outcome scores (IKDC, Lysholm), patient satisfaction, and adverse events.

## 3. Study Design

This is a single-center, prospective, cohort pilot study. Fifty-three patients undergoing ACL reconstruction with BPTB autograft were included. Patients were divided into two groups: Group 1 (PRF group, n=24) with PRF applied at the donor site, and Group 2 (Control group, n=29) with standard closure without PRF. Patients were followed for 12 months postoperatively.

## 4. Eligibility Criteria

Inclusion Criteria:

- Age 18–40 years
- Isolated ACL rupture confirmed by MRI and clinical examination
- Planned ACL reconstruction with BPTB autograft
- Written informed consent provided

Exclusion Criteria:

- Previous surgery on the affected knee
- Associated ligament injuries requiring additional reconstruction
- Outerbridge grade III–IV cartilage damage outside donor site
- Systemic diseases interfering with healing (e.g., diabetes, autoimmune disease)

Study Protocol Title: Impact of Platelet-Rich Fibrin on Donor Site Regeneration and Functional Recovery after ACL Reconstruction with BPTB Autograft

Version: 01, 18 September 2020

- Active infection
- Refusal or inability to consent

## 5. Interventions

Group 1 (PRF group): Intraoperatively prepared autologous PRF was applied to the donor site after graft harvesting.

Group 2 (Control group): Standard closure without PRF application.

## 6. Outcome Measures

Primary Outcome: Absence of sensory deficit at the donor site 12 months after surgery.

Secondary Outcomes:

- MRI assessment of donor site healing
- Functional outcome scores (IKDC, Lysholm)
- Patient-reported satisfaction
- Adverse events related to surgery or PRF application

## 7. Study Procedures and Follow-up

Patients were evaluated at baseline, and postoperatively at 4, 8, and 12 months. Clinical assessments included sensory testing, range of motion, and functional scores. MRI was performed to evaluate donor site healing. Patient satisfaction was assessed at 12 months.

## 8. Ethics and Regulatory Considerations

The study was approved by the Ethics Committee of the Faculty of Medicine, University of Belgrade (Approval No. 17/VI-3). Written informed consent was obtained from all participants prior to enrollment. The study adhered to the Declaration of Helsinki principles.

## 9. Statistical Analysis

Descriptive statistics were used to summarize baseline characteristics. Chi-square test and t-tests were used to compare categorical and continuous variables between groups. A post-hoc power calculation for the primary endpoint was performed based on the 12-month results. All analyses were conducted using standard statistical software.

Study Protocol Title: Impact of Platelet-Rich Fibrin on Donor Site Regeneration and Functional Recovery after ACL Reconstruction with BPTB Autograft

Version 01, 21 September 2020

COVER PAGE

Study Protocol Title : Impact of Platelet-Rich Fibrin on Donor Site Regeneration and Functional Recovery after ACL Reconstruction with BPTB Autograft

Version/Date: Version 01, 21 September 2020

NCT number: Not Available

Statistical Analysis Plan (SAP)

Study title: Sensory deficit following anterior cruciate ligament reconstruction with bone patellar-tendon bone autograft: platelet-rich fibrin (PRF) could provide a solution

Design: Single-center prospective cohort pilot study with two parallel groups (PRF / Vivostat group vs. Standard group) and repeated follow-up measurements

Sample size: 53 male patients (Vivostat n = 24; Standard n = 29)

Primary endpoint: Sensory deficit at the donor site over time (4, 8 and 12 months)

Secondary endpoints: Subjective knee function scores (Modified Cincinnati, IKDC, Tegner Lysholm, Tegner Activity Score); demographic and perioperative characteristics; safety

1. Analysis Populations

- **Full Analysis Set (FAS):** All patients who met inclusion criteria, underwent ACL reconstruction with BPTB autograft, were assigned to one of the two cohorts (Vivostat vs. Standard) and had at least one postoperative follow-up assessment. All efficacy analyses (sensory deficit and subjective scores) will be based on the FAS.
- **Safety Set:** All operated patients for whom group assignment (Vivostat vs. Standard) is known. Safety (complications, adverse events) will be summarized descriptively in this set.

No separate per-protocol analysis is planned because all 53 included patients completed follow-up according to the study results.

2. Endpoints

2.1 Primary endpoint

The **primary endpoint** is the **presence of sensory deficit at the donor site** at postoperative follow-ups:

- Sensory deficit is assessed in a predefined skin area lateral to the incision and coded as a binary variable:
 - **0 = no sensory deficit** (normal perception in all points);
 - **1 = sensory deficit present** (numbness or altered sensation in more than three tested points).

Measurements are performed at:

Study Protocol Title: Impact of Platelet-Rich Fibrin on Donor Site Regeneration and Functional Recovery after ACL Reconstruction with BPTB Autograft

Version 01, 21 September 2020

- 4 months after surgery,
- 8 months after surgery,
- 12 months after surgery.

The primary focus of the analysis is:

1. **Between-group comparison** (Vivostat vs. Standard) of the proportion of patients with sensory deficit (0/1) at each time point, with special emphasis on the 12-month result.
2. **Within-group change over time** (4 vs. 8 vs. 12 months) in the proportion of patients with sensory deficit.

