6.1 Between-group comparisons at each follow-up

At 4, 8 and 12 months, the proportions of patients with and without sensory deficit (0 vs. 1) will be summarized for each group.

- For **between-group comparisons** (Vivostat vs. Standard) at each time point, a **Chi-squared test** will be performed when expected cell counts are adequate. If assumptions are not met, **Fisher's exact test** may be used.
- In the current dataset, statistical significance is expected at 8 months ($p < 0.05$) and 12 months ($p < 0.01$), but not at 4 months.

Results will be reported as in Table 3, with counts, percentages, and p-values.

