6.2 Within-group change over time

To assess changes in sensory deficit over time (4 vs. 8 vs. 12 months):

- For **overall comparison across the three time points** within each group and in the total sample, **Cochran's Q test** will be used.
- If Cochran's Q test is significant, **pairwise McNemar's χ^2 tests** will be used to compare:
 - 4 vs. 8 months,
 - 4 vs. 12 months,
 - 8 vs. 12 months.

Bonferroni correction will be applied for these three pairwise tests ($\alpha = 0.05/3 \approx 0.0167$). The corrected p-values and interpretation will be presented as in Table 4.

These analyses identify the postoperative interval with the most pronounced sensory recovery (in the current study: mainly between 4 and 8 months in the Vivostat group, with stabilization thereafter).

7. Power Calculation

Study Protocol Title: Impact of Platelet-Rich Fibrin on Donor Site Regeneration and Functional Recovery after ACL Reconstruction with BPTB Autograft

Version 01, 21 September 2020

After completing data collection, a **post-hoc power calculation** for the primary endpoint at 12 months will be performed:

- Observed proportions without sensory deficit at 12 months:
 - Vivostat group: 79% (0.79),
 - Standard group: 34% (0.34).
- Group sizes: $n_1 = 24$ (Vivostat), $n_2 = 29$ (Standard).
- Test: two-sided pooled z-test for difference in proportions, $\alpha = 0.05$.

The achieved power for detecting this difference is **0.93**, indicating that, despite being a pilot study, the sample size was sufficient to detect the observed effect size at 12 months with high probability.

This power calculation is descriptive and does not change the interpretation of the primary analysis.

8. Handling of Missing Data

In the conducted study all 53 patients completed follow-up; therefore, **no imputation of missing data** was necessary.

For the purposes of the statistical plan:

- In the event of missing follow-up data for future or extended analyses, only **complete-case analyses** will be performed (patients with available data for a given endpoint).
- The number and proportion of patients with missing data for each time point and endpoint would be reported descriptively.
- No multiple imputation or advanced methods are planned, given the pilot nature and small sample size.

9. Sensitivity and Exploratory Analyses

Given the modest sample size, no predefined subgroup analyses are planned. However, exploratory analyses could include:

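### The two codes of the binary primary endpoint leave out patients with 1 to 3 altered points, and no rule for them is given

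*SAP*

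**What the plan says.** SAP 2.1 describes the primary endpoint this way: "Sensory deficit is assessed in a predefined skin area lateral to the incision and coded as a binary variable". Code 0, no deficit, is defined as "normal perception in all points". Code 1, deficit present, is defined as "numbness or altered sensation in more than three tested points". The number of points tested is not stated.

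SAP 6.1 then treats every patient as one or the other: at each visit "the proportions of patients with and without sensory deficit (0 vs. 1) will be summarized for each group". SAP 6.2 takes the same variable into Cochran's Q and McNemar's tests. SAP 7 gives "Observed proportions without sensory deficit at 12 months" as 79% (Vivostat, n = 24) and 34% (Standard, n = 29).

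The protocol is less specific. Protocol 6 names the outcome as "Absence of sensory deficit at the donor site 12 months after surgery", and Protocol 7 says only "Clinical assessments included sensory testing, range of motion, and functional scores". Neither gives a threshold or a number of points.

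**The concern.** A binary endpoint needs two codes that together cover every possible result. Here one boundary sits at zero altered points and the other at four or more, with a gap between them. The wording of code 0 suggests that any altered point is a deficit; the wording of code 1 suggests that up to three are tolerated. The text does not choose between these readings.

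The primary result therefore cannot be reproduced from the plan: 79% and 34% could mean no altered point, or at most three. The documents describe no blinding of the assessor, so nothing in them excludes case-by-case coding. The same variable enters every between-group test and all the within-group tests over time.

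**Working it through.** **1. The two codes against every possible count (SAP 2.1)**

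| Altered points | Meets code 0? | Meets code 1? |
|---|---|---|
| 0 | yes | no |
| 1, 2 or 3 | no | no |
| 4 or more | no | yes |

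No other section fills the middle row. Protocol 2, 6 and 7 and SAP 6.1 and 6.2 add no threshold. SAP 8 deals with missing follow-up, not with results that fit no code.

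**2. The plan's own figure**

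Inputs from SAP 7: p1 = 0.79, n1 = 24; p2 = 0.34, n2 = 29; two-sided pooled z-test, alpha 0.05.

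- Pooled proportion = (24 × 0.79 + 29 × 0.34)/53 = 0.544
- SE under the null = √[0.544 × 0.456 × (1/24 + 1/29)] = 0.137
- SE under the alternative = √[0.79 × 0.21/24 + 0.34 × 0.66/29] = 0.121
- Power = Φ[(0.45 − 1.96 × 0.137)/0.121] = Φ(1.49) = 0.93

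The stated 0.93 reproduces. It takes the 0/1 coding as given, so it does not bear on the gap.

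**3. Were uncodable patients left out?**

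- Standard: among all counts with a denominator of 29 or less, only 10/29 (34.5%) rounds to 34%.
- PRF: 79% with the stated n1 = 24 is 19/24 (79.2%).
- SAP 8 says that all 53 completed follow-up.

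So all 53 appear to have been given a code at 12 months.

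**4. Starting table**

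Without deficit: 19/24 vs 10/29. Difference = 79.2% − 34.5% = 44.7 points (Newcombe 95% CI 17.9 to 63.3). Chi-square = 53 × (19 × 19 − 5 × 10)²/(24 × 29 × 29 × 24) = 10.58, p = 0.0011. With Yates correction p = 0.0029; Fisher p = 0.0020. The smallest expected count is 24 × 24/53 = 10.9, so SAP 6.1 points to the chi-square test.

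**5. What recoding would do**

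The number of patients with 1 to 3 altered points is not in the documents. The shares and counts below are assumptions. If those patients were coded 0, the stricter reading moves some 0s to 1; if they were coded 1, the more lenient reading moves some 1s to 0.

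*Assumption A: about the same share recoded in both arms, rounded to whole patients*

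| Recode | Without deficit, PRF vs Standard | Difference in points (95% CI) | p: chi-square / Yates / Fisher |
|---|---|---|---|
| 20% of 0s to 1 | 15/24 vs 8/29 | 34.9 (8.1 to 55.7) | 0.011 / 0.023 / 0.014 |
| 30% of 0s to 1 | 13/24 vs 7/29 | 30.0 (3.8 to 51.6) | 0.025 / 0.050 / 0.045 |
| 40% of 0s to 1 | 11/24 vs 6/29 | 25.1 (−0.1 to 47.1) | 0.051 / 0.098 / 0.077 |
| 20% of 1s to 0 | 20/24 vs 14/29 | 35.1 (9.2 to 54.7) | 0.008 / 0.018 / 0.010 |
| 30% of 1s to 0 | 21/24 vs 16/29 | 32.3 (7.6 to 51.7) | 0.011 / 0.024 / 0.016 |
| 40% of 1s to 0 | 21/24 vs 18/29 | 25.4 (1.5 to 45.3) | 0.037 / 0.076 / 0.060 |

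*Assumption B: all recoded patients in one arm, in the direction that shrinks the difference (worst case)*

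| Recode | Without deficit, PRF vs Standard | p: chi-square / Yates / Fisher |
|---|---|---|
| 2 PRF, 0 to 1 | 17/24 vs 10/29 | 0.008 / 0.018 / 0.013 |
| 3 PRF, 0 to 1 | 16/24 vs 10/29 | 0.020 / 0.040 / 0.028 |
| 4 PRF, 0 to 1 | 15/24 vs 10/29 | 0.042 / 0.079 / 0.056 |
| 5 PRF, 0 to 1 | 14/24 vs 10/29 | 0.083 / 0.14 / 0.10 |
| 2 Standard, 1 to 0 | 19/24 vs 12/29 | 0.006 / 0.013 / 0.011 |
| 3 Standard, 1 to 0 | 19/24 vs 13/29 | 0.011 / 0.024 / 0.013 |
| 5 Standard, 1 to 0 | 19/24 vs 15/29 | 0.038 / 0.074 / 0.048 |
| 6 Standard, 1 to 0 | 19/24 vs 16/29 | 0.066 / 0.12 / 0.085 |

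The effect on the Cochran Q and McNemar tests cannot be computed, because the 4- and 8-month counts are not given.

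**The case against.** The strongest reply is that no effect has been shown. Nothing in the documents says that any patient had 1 to 3 altered points at any visit, and the illustration itself shows that an even recode of up to about 30% leaves uncorrected chi-square p below 0.05. This stands: certainty attaches to the gap in the definition, not to any error in the reported result.

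The claim that everyone was coded is also firmer for one arm than the other. From the percentage alone, 79% could be 19/24, 15/19 or 11/14. For PRF, completeness rests on the group size printed beside the percentage and on the statement that all 53 completed follow-up. That is enough to say that all appear to have been coded, but the percentage alone does not prove it.

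Two limits of the tables also stand. Rounding matters: 30% of five PRF patients is 1.5, taken as 2. Taken as 1, the row becomes 20/24 vs 16/29, a difference of 83.3% − 55.2% = 28.2 points before rounding of the percentages. And assumption B shows only the unfavourable direction. Recoding the other way would widen the gap; for example, one Standard patient moved from 0 to 1 gives 19/24 − 9/29 = 48.1 points. None of this supplies the missing rule.

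**Conclusion.** The concern holds. The primary endpoint is called binary, but its coding rule cannot be applied as written to a patient with 1 to 3 altered points, and neither document says what was done with such patients.

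The effect on the 12-month result is conditional on how many there were, and it is nil if there were none. If they were spread evenly over the arms, significance at 0.05 by the uncorrected chi-square test is fairly robust up to about a 30% recode, while the difference falls by about 12 to 15 points with the rounding used in the table (44.7 − 32.3 = 12.4; 44.7 − 30.0 = 14.7). In the one-arm worst case, the p < 0.01 level quoted in SAP 6.1 is lost after 3 patients in either arm by uncorrected chi-square, or 2 by Yates or Fisher. The 0.05 level is lost after 4 to 5 PRF or 5 to 6 Standard patients, depending on the test.

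These figures assume 19/24 and 10/29 as the starting counts.

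**What to change.** - Make the two codes in SAP 2.1 complementary, and state how many points are tested.
- State which rule was applied to 1 to 3 altered points in the reported 79% and 34%.
- Where point-level records exist, tabulate 0, 1 to 3, and more than 3 altered points by group and visit.
- Report the 12-month comparison, with the difference and its confidence interval, under both codings: deficit as more than three altered points, and deficit as any altered point. Showing both matters because the SAP already quotes the 12-month results, so a cut-off chosen now could be chosen by its result.
- Say whether the chi-square test is continuity-corrected, since several of the borderline cases turn on it.
- If point counts were not kept, say so as a limitation of the primary endpoint.

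With point-level records, the cost is a wording change, one extra table and one repeated test. Without them, it is a sentence of limitation. The sponsor should accept in advance that the percentages and p-value may become less favourable, though they could also move the other way.

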2.2 Secondary endpoints

Secondary endpoints include:

- **Subjective functional scores:**
 - Modified Cincinnati score (continuous),
 - IKDC score (continuous),
 - Tegner Lysholm score (continuous),
 - Tegner Activity Score (ordinal/continuous).Each is measured preoperatively (baseline) and at 12 months postoperatively.
- **Demographic and perioperative characteristics:**
 - Age (years),
 - Body mass index (BMI, kg/m²),
 - Time from injury to surgery (months),
 - Length of hospitalization (days).

These are used to describe and compare the two groups at baseline.

- **Safety endpoints:** Clinical complications (infection, wound problems, thromboembolic events, range of motion restriction, graft rupture) observed during follow-up. These are summarized descriptively (frequency and percentage in each group).

3. General Statistical Principles

- All statistical tests will be **two-sided**.
- The nominal significance level is **p < 0.05**.
- For multiple pairwise comparisons of the same endpoint (e.g., sensory deficit across the three follow-up time points), **Bonferroni correction** will be applied ($\alpha_{\text{corrected}} = 0.05 / \text{number of comparisons}$).

Study Protocol Title: Impact of Platelet-Rich Fibrin on Donor Site Regeneration and Functional Recovery after ACL Reconstruction with BPTB Autograft

Version 01, 21 September 2020

- Continuous variables will be summarized as **mean, standard deviation, median and range**.
- Categorical variables will be summarized as **absolute frequencies and percentages**.
- The distribution of continuous variables will be assessed using the **Kolmogorov–Smirnov** and **Shapiro–Wilk** tests. Because most continuous variables deviate from normality or sample sizes are modest, **non-parametric tests** will be used for between- and within-group comparisons.

All analyses will be performed using **R software**, version 4.3.1 (2023-06-16).

4. Baseline Comparisons

Baseline comparability of the Vivostat and Standard groups will be assessed for:

- age, BMI, time from injury to surgery, length of hospitalization.

Since these are continuous variables, they will be compared between groups using the:

- **Wilcoxon rank-sum test** (Mann–Whitney U test).

Results will be presented as in Table 1 (mean, SD, median, range, and p-values). These analyses are descriptive and serve to document the similarity of groups at baseline in this non-randomized cohort.

5. Analysis of Subjective Functional Scores

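### The protocol has one primary outcome, at 12 months; the SAP makes three visits and within-group change primary and does not state whether the three between-group tests are corrected.

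*SAP*

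**What the plan says.** **Protocol.** Section 2 gives the primary objective as "To evaluate the effect of PRF application on sensory disturbances at the donor site 12 months after ACL reconstruction". Section 6 gives the primary outcome as "Absence of sensory deficit at the donor site 12 months after surgery". Section 9 adds that "A post-hoc power calculation for the primary endpoint was performed based on the 12-month results".

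**SAP, primary endpoint.** The cover summary gives "Sensory deficit at the donor site over time (4, 8 and 12 months") as the primary endpoint. Section 2.1 lists two items under the primary focus. The first is a between-group comparison "of the proportion of patients with sensory deficit (0/1) at each time point, with special emphasis on the 12-month result"; the second is change over time within each group. Section 7 nevertheless computes power for the primary endpoint at 12 months only, at alpha 0.05.

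**SAP, multiplicity.** Section 3 sets a Bonferroni rule that begins "For multiple pairwise comparisons of the same endpoint (e.g., sensory deficit across the three follow-up time points"). Section 6.1 specifies a chi-squared test (Fisher if needed) at each visit and gives no corrected alpha. It then says "In the current dataset, statistical significance is expected at 8 months", with p below 0.05, and at 12 months with p below 0.01. Section 6.2 says "Bonferroni correction will be applied for these three pairwise tests", at 0.0167; those are the within-group McNemar tests.

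**The concern.** The two documents do not agree on what is primary, and the SAP does not agree with its own section 7. Giving 12 months special emphasis does not designate it as the single confirmatory test. A reader of the SAP can treat significance at any of the three visits as a primary finding, and cannot tell what threshold applies.

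Two statements borrow a primary status that the protocol never gave them. One is significance at 8 months (SAP 6.1). The other is the SAP 6.2 description of recovery in the Vivostat group as falling mainly between 4 and 8 months and then levelling off. The second comes from tests that contain no comparison with control, so the pattern can appear in one group when PRF does nothing.

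**Working it through.** **1. The plan's own figure.** Inputs from SAP 7: 0.79 and 0.34 without deficit, n = 24 and 29, two-sided alpha 0.05, pooled z-test.

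- Pooled rate = (24 × 0.79 + 29 × 0.34)/53 = 0.544
- SE under the null = √[0.544 × 0.456 × (1/24 + 1/29)] = 0.1374
- SE under the alternative = √[0.79 × 0.21/24 + 0.34 × 0.66/29] = 0.1210
- Power = Φ[(0.45 − 1.960 × 0.1374)/0.1210] = Φ(1.492) = 0.932

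The stated 0.93 reproduces. It belongs to a single test at 12 months and alpha 0.05. If three between-group tests were co-primary under Bonferroni, alpha would be 0.05/3 = 0.0167 and power at 12 months Φ[(0.45 − 2.394 × 0.1374)/0.1210] = Φ(0.999) = 0.84.

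**2. Does the Bonferroni rule reach the between-group tests?** The rule in SAP 3 concerns pairwise comparisons across follow-up times. That describes 4 v 8, 4 v 12 and 8 v 12 months, which is where SAP 6.2 applies it. SAP 6.1 is silent on correction and cites 0.05 at 8 months; SAP 7 uses 0.05 at 12 months. The rule fits the McNemar tests best, but nothing in SAP 3 excludes the between-group tests.

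**3. Error rate if they are uncorrected.** For three independent tests of exact size 0.05 it is 1 − 0.95³ = 0.143. Visits are correlated and the tests are discrete, so this was simulated: no PRF effect, n = 24 and 29, and three binary outcomes from correlated latent normals. The documents give no 4- or 8-month rates and no correlations, so these are assumptions. Five sets of no-deficit rates were used (0.30/0.45/0.50; 0.15/0.35/0.50; 0.34/0.34/0.34; 0.20/0.45/0.55; 0.10/0.25/0.34), with latent correlation from 0 to 0.97.

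| Test | At least one p < 0.05 in three visits | 12 months alone |
|---|---|---|
| Pearson | 9.5–15.8% | 5.1–5.7% |
| Fisher | 7.0–10.7% | 3.0–3.8% |
| Yates | 4.5–7.6% | 2.4–2.9% |

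The rate generally falls as the visits become more correlated. Pearson can pass 14.3% because its actual size at these group sizes is slightly above 5%.

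**4. The 12-month result.** Only 19/24 (79.2%) rounds to 79%; 18/24 is 75.0% and 20/24 is 83.3%. Only 10/29 (34.5%) rounds to 34%; 9/29 is 31.0% and 11/29 is 37.9%.

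- Pearson χ² = 53 × (19 × 19 − 5 × 10)²/(24 × 29 × 29 × 24) = 10.58, p = 0.0011
- Yates χ² = 53 × (311 − 26.5)²/484,416 = 8.86, p = 0.0029
- Fisher p = 0.0020
- Difference = 0.792 − 0.345 = 0.447. Newcombe 95% CI, from Wilson limits 0.595–0.908 and 0.199–0.527: lower 0.447 − √[(0.792 − 0.595)² + (0.527 − 0.345)²] = 0.179; upper, by the matching formula, 0.633

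All three p-values are below 0.0167. The 8-month p-value is known only to be below 0.05, so whether it is below 0.0167 cannot be told.

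**5. The within-group pattern.** Both groups were given identical assumed recovery (0.30/0.45/0.50), over the same correlations. The SAP 6.2 sequence was applied: Cochran's Q below 0.05, 4 v 8 McNemar below 0.0167, 8 v 12 not significant. This appears in the PRF group and not in the control group in about 2–4% of trials with continuity-corrected McNemar, and in 6–11% without the correction.

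**The case against.** The strongest reply is that SAP 3 already covers the case: its example is sensory deficit across three follow-up times and its divisor is the number of comparisons, which could mean three two-group tests. That reading is open, so a reader who concludes that the SAP leaves these tests uncorrected goes further than the text allows. It does not rescue the plan. On that reading the 8-month result needs p below 0.0167, and the SAP shows only p below 0.05.

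Second, the inflation may be small. SAP 6.1 does not name the chi-square version. SAP 3 specifies R, whose standard chi-square function applies Yates' correction to 2×2 tables by default; that gives about 5–8%. This stands. The pooled z-test in SAP 7 corresponds to Pearson, so the higher range cannot be excluded.

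Third, SAP 6.2 uses the within-group tests to locate an interval of recovery, gates the McNemar tests behind Cochran's Q and corrects them. It does not offer them as proof that PRF works. This also stands. The problem is their place under the primary focus, where a reader could take a pattern described for the Vivostat group as a treatment effect.

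**Conclusion.** The disagreement over the primary time point is plain in the text and needs correcting. The multiplicity gap is an ambiguity, not a stated absence of correction. Its size, if the tests are uncorrected, is about 10–16% (Pearson), 7–11% (Fisher) or 5–8% (Yates), and rests on assumed visit rates and correlations. The within-group figures of 2–4% and 6–11% rest on one assumed recovery curve.

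What is exposed is the 8-month claim. Two stronger inferences should be resisted:

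- That the 12-month result falls. Its p-value passes 0.05 and 0.0167 alike. Equally, passing them does not establish a PRF effect: SAP 4 describes a non-randomised cohort, and a multiplicity check says nothing about confounding.
- That 12 months was prespecified and the SAP later moved away from it. The protocol itself is in the past tense, gives final group sizes (section 3) and reports a completed post-hoc power calculation (section 9). The documents cannot show which time point was chosen before results were known.

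**What to change.** - In the SAP cover summary, 2.1 and 6.1, name the 12-month between-group comparison as the sole primary analysis at two-sided alpha 0.05, in line with Protocol 2 and 6 and SAP 7. No correction is then needed and the 0.93 still describes the primary test.
- Report the 4- and 8-month between-group comparisons as secondary and descriptive: difference in proportions with 95% CI, no claim of significance. Replace the sentence in 6.1 that expects significance at 8 months.
- Label the Cochran Q and McNemar tests descriptive and not evidence of a PRF effect.
- Under SAP 10, disclose that this was settled after results were known. State also that the SAP (5, 6.1, 6.2, 7) and the protocol (3, 7, 9) already reflect the completed study, so prespecification of 12 months cannot be shown from them.

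The cost is SAP wording, two confidence intervals from counts the trial already has, and a short disclosure. No new data are needed. The drawbacks are that the 8-month result can no longer be called significant and that the change is itself post hoc.
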